### **5.5.2. Alcohol Restrictions**

Patients will limit alcohol consumption throughout the course of the study. Alcohol is limited to no more than 2 units per day (unit: 1 glass of wine [approximately 125 mL] = 1 measure of spirits [approximately 1 fluid ounce] =  $\frac{1}{2}$  pint of beer [approximately 284 mL]) for the duration of the study.

### **5.5.3. Antibiotic Compliance**

Patients who require prophylactic antibiotics after randomization to cemdisiran or placebo (see Section [5.3.2.1](#)) per local standard of care will undergo antibiotic compliance checks. Antibiotic compliance checks will be performed at the time points in the Schedule of Assessments. Antibiotic dose adjustments will be permitted in the case of renal impairment. All dose adjustments must comply with the manufacturer's instructions.

## 6. STUDY ASSESSMENTS

The Schedule of Assessments is provided in [Table 1](#) and [Table 2](#).

### 6.1. Screening Assessments

An ICF approved by the appropriate Institutional Review Board (IRB)/Independent Ethics Committee (IEC) must be signed by the patient (or legal guardian) before the Screening procedures are initiated. All patients (or their legal guardians) will be given a copy of the signed and dated ICF.

Patients will be screened to ensure that they meet all the inclusion criteria and none of the exclusion criteria. Rescreening of patients is permitted with consultation of the Medical Monitor; see Section [6.1.1](#).

Patient demographic data and medical history/disease history will be obtained. In particular, the MEST-C score and degree of IgG, IgA, IgM, C3, C1q, C4d and C5b-9 stains will be obtained from pathology reports, if available, and documented. Any changes to medical history occurring between the Screening assessment and Day 1 will be updated prior to study drug administration. Additional screening assessments include a full physical examination (with emphasis on presence/degree of edema), collection of vital signs, height, weight and body mass index (BMI), 12-lead electrocardiogram (ECG), clinical laboratory assessments, pregnancy, 24-hours urine proteinuria assessment (from a single valid collection; see Section [6.4.1.1](#)), eGFR, urinalysis and ADA and CIC assessments. Vaccination records will also be checked for compliance with national/local guidelines for pneumococcal and Hib vaccinations.

#### 6.1.1. Rescreening

A patient who does not meet all study eligibility criteria due to a transient condition observed at Screening (eg, prohibited medications that were subsequently discontinued) will be allowed to return for rescreening (once only). A patient will be re-consented if rescreening occurs outside of the 90-day screening window. In this case, all screening procedures must be repeated.

#### 6.1.2. Retesting

If in the Investigator's judgement, the laboratory abnormalities at Screening or in the run-in period are likely to be transient, then laboratory tests may be repeated. The Investigator's rationale is to be documented. Laboratory values can be retested once during Screening or the run-in period as long as the patient can be evaluated for eligibility and randomized within the allowed Screening or run-in period. Two retests will be permitted for hematuria during Screening, if the first test is negative.

## 6.2. Run-in Period

During the 14-week run-in period, the following will be performed at time points specified in the Schedule of Assessments ([Table 1](#)): Hib and pneumococcal vaccinations (if required at Screening per national/local guidelines; vaccination should occur prior to Week-2), vital signs, clinical laboratory assessments, pregnancy test, 24-hour urine proteinuria assessment (from 2 single valid collections; see Section [6.4.1.1](#)), urinalysis for hematuria, spot urine for proteinuria, and eGFR. Clinical laboratory tests will be performed centrally; however, eGFR will also be

assessed locally at the end of the run-in period (Week-2) to facilitate assessment of patient eligibility and administer meningococcal vaccination on the same day. Meningococcal vaccines should be administered only if patient eligibility for randomization is confirmed and after urine collections are completed.

Sites are encouraged to discuss study information with the patients again at the end of the run-in period.

### **6.3. Baseline Assessments (Treatment Period)**

Prior to dosing on Day 1, patients will be reassessed for eligibility and blood and urine samples for clinical laboratory assessments and exploratory analyses collected, including blood samples for complement activity tests (CAP/CCP), C5 analysis, PK, ADA and CIC.

In addition, prior to administration of study drug, the following assessments will be performed: full physical examination, body weight and height, vital signs, ECG, urine pregnancy test, eGFR assessment, and urinalysis.

Collection of blood and urine samples for PK analysis on Day 1 will be performed as outlined in [Table 3](#).

### **6.4. Efficacy Assessments**

#### **6.4.1. Proteinuria**

Primary efficacy will be assessed by determining the percent change from baseline in 24 hour proteinuria (g/24-hour) after 32 weeks of treatment. 24 hour urine samples for determination of proteinuria will be collected throughout the study as outlined in the Schedules of Assessments and will be analyzed by a central laboratory.

##### **6.4.1.1. 24-Hour Urine Collection**

Patients will be required to provide two separate valid 24-hour urine collections 2 weeks prior to randomization (to assess eligibility after the run-in period) and at Week 32 (to assess the primary endpoint). Patients will also be asked to provide a single valid 24-hour urine sample for other 24-hour urinary assessments outlined in the Schedule of Assessments. Rigorous exercise and significant change in diet (in particular salt intake) should be avoided within 48 hours before collection of 24-hour urine samples, whenever possible. The two valid 24-hour urine samples may be collected within 2 weeks before assessment is due while the one valid 24-hour urine sample may be collected within one week before the assessment takes place. If any of the collections do not meet validity criteria outlined below, then repeat collections must be scheduled within the time frames outlined above to assure the minimum number of valid collections required for each of the study time points. The duration of collection and volume of urine in the collection will be recorded in the eCRF. In addition to protein, albumin, sodium and creatinine will also be quantified in each of the 24-hour urine samples. Both protein/creatinine (UPCR) as well as albumin/creatinine ratios (UACR) will also be calculated in an aliquot of the 24-hour urine collection.

Completeness of the 24-hour urine collection can be estimated from rate of creatinine excretion. Normal values of creatinine excretion vary with age and body weight. An aliquot of the 24-hour

urine collection will be used to determine urinary creatinine content to determine if the 24-hour urine collections need to be repeated. Hence, a 24-hour urine collection will only be considered valid if all the following criteria are met, otherwise a repeat urine collection will be required:

- The collection is between 22-26 hours in duration between the initial discarded void and the last void or attempt to void.
- No voids are missed between the start and end time of the collection as indicated by the patient's urine collection diary.
- The 24-hour creatinine content is within 25% of expected range as estimated by the following formula:  $[(140\text{-age}) \times \text{weight}]/5000$ , where weight is in kilograms. This result is multiplied by 0.85 in women.[\[Ix 2011\]](#)
- In case of need of two valid samples, the maximum variation in total 24-hour urine creatinine between the two urine collections must be <25%.

Primary efficacy will be evaluated by comparing the percent change from baseline in 24-hour proteinuria (g/24-hours) at Week 32 in patients treated with cemdisiran versus those treated with placebo.

Secondary and exploratory efficacy assessments include comparisons of the proportion of patients with partial or complete clinical remission, respectively, as measured by the amount of urine protein (UP) in a 24-hour urine sample. Partial clinical remission is defined as having UP <1 g/24-hours and complete clinical remission is defined as UP <0.3 g/24-hours. Each will be assessed at Week 32.

Additionally, using 24-hour samples, the change from baseline in the UP/creatinine ratio (UPCR) will be evaluated as a secondary endpoint and the change from baseline in urine albumin/creatinine ratio (UACR) at Week 32 as an exploratory endpoint.

#### **6.4.1.2. Spot Urine Collection**

Urinary protein, albumin and creatinine levels from spot urine collections prior to dosing will also be measured to assess the effect of cemdisiran on urinary protein/creatinine (UPCR) and albumin/creatinine (UACR) as outlined in the Schedule of Assessments.

The change from baseline in UPCR at Week 32 will be evaluated in spot urine samples. Spot urine samples will be collected at the time points outlined in the Schedule of Assessments ([Table 1](#)).

#### **6.4.2. Hematuria**

Hematuria from spot urine collections will also be evaluated to assess the effect of cemdisiran on disease course in patients with IgAN. The degree of hematuria will be assessed by examination of the spun urine sediment by microscopy (RBC/hpf). Single void collections for random urine sample for hematuria evaluation should be collected. If the investigator determines that the hematuria is transient due to menses in women or exercise, the sample may need to be repeated.

Random spot urine samples for hematuria measurement will be collected throughout the study as outlined in the Schedule of Assessments and will be analyzed by a central laboratory. On dosing days, samples should be collected prior to study drug administration, if applicable.

#### **6.4.3. Changes in Renal Function**

Changes in renal function will be monitored using measurements of serum creatinine and eGFR (mL/min/1.73m^2) as outlined in the Schedule of Assessments. The calculation will be based on the Chronic Kidney Disease Epidemiology Collaboration (CKD-EPI) formula for all patients. For assessment of eligibility at the last visit of run-in period, 2 weeks prior to randomization, local lab can be utilized. This will allow evaluation for eligibility on the same day. A sample will also be sent to central lab.

Renal function will also be estimated as creatinine clearance based on the 24-hour urine collection. The creatinine clearance is a widely used test to estimate the GFR using the following formula:

$$\text{GFR} = [\text{UCr} \times \text{V}] / \text{SCr}$$

SCr is the serum creatinine concentration and the value assessed closest to collection of 24-hour urine collection will be utilized for purpose of above calculation. UCr is the urine creatinine concentration and V is the urine flow rate or volume.

Blood and urine samples for renal function assessments will be collected prior to administration of cemdisiran or placebo on dosing days, if applicable.

The change from baseline in eGFR will be measured throughout the course of the study. In addition, the slope of eGFR will be computed for the first 32 weeks and the entire study period (including the OLE).

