## 2. OBJECTIVES AND ENDPOINTS

Objectives	Endpoints
Primary	

To evaluate the effect of cemdisiran on proteinuria in adult patients with immunoglobulin A nephropathy (IgAN)

	

Percent change from baseline in 24-hour proteinuria (g/24-hours) at Week 32

Secondary	

Percent of patients with partial clinical remission (urine protein [UP] <1.0 g/24-hours) at Week 32

Percent of patients with >50% reduction in 24-hour proteinuria at Week 32

Change from baseline in urine protein/creatinine ratio (UPCR; in g/g) as measured in 24-hour urine at Week 32

Change from baseline in UPCR as measured in a spot urine at Week 32

Change from baseline in hematuria at Week 32 (red blood cells per high powered field [RBC/hpf])

Frequency of adverse events (AEs)

Exploratory	

To evaluate the effect of cemdisiran on renal function parameters

To evaluate the pharmacodynamic (PD) effect of cemdisiran in adult patients with IgAN

To characterize the pharmacokinetics (PK) of cemdisiran and relevant metabolites in plasma and urine in adult patients with IgAN

To evaluate the effect of cemdisiran on serum and urine markers of complement activation, renal damage and inflammation

To assess the incidence of antidrug antibodies (ADA)

 

Change from baseline in estimated glomerular filtration rate (eGFR) at Week 32

The slope of eGFR computed for the first 32 weeks using all assessments during the period

The slope of eGFR computed for the entire study period including the open label extension using all assessments during the study.

Change from baseline in creatinine clearance at Week 32

Percent of patients in full clinical remission (Urine Protein [UP] <0.3 g/24-hours) at Week 32

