During the run-in period, patients will visit the study center 14, 8, and 2 weeks prior to randomization (Weeks 0, 6 and 12 of the run-in period). Patients will then return to the study center every 4 weeks after the start of study drug treatment period. The primary endpoint will be assessed at the end of treatment at Week 32.

At the end of treatment (Week 32), patients in the two treatment arms will enter the optional OLE period where they will receive cemdisiran at a dose of 600 mg every 4 weeks in combination with standard of care for 52 weeks. The first study drug administration of the OLE will be administered at Week 36. Patients will return to the study center at Week 40 and every 8 weeks thereafter during the OLE. Home visits, where locally feasible, may be arranged for cemdisiran administration in between 8-weekly study center visits (Weeks 44, 52, 60, 68 and 76), unless patients are required to visit the study center as judged necessary by the Investigator, or if home visits cannot be arranged. An end of treatment (EOT) visit will occur at Week 80 (OLE EOT) and an end of study (EOS) or early termination (ET) visit will be completed at Week 84 (OLE EOS/ET). For patients who complete the treatment period only who do not consent to continue to participate in the study in the OLE period, the EOS/ET visit will be at Week 36.

Patients will return to the clinical study center for safety follow-up visits approximately 13, 26, 39 and 52 weeks after the EOS/ET visit (regardless if EOS/ET visit is at Week 36 or Week 84), unless enrolled in another study with cemdisiran. Home visits, where locally feasible, may be arranged during safety follow-up at 13 and 39 weeks after the EOS/ET visit (regardless if EOS/ET visit is at Week 36 or Week 84).

Regular reviews of safety and tolerability data will be performed by an independent data monitoring committee (DMC) throughout the study with the primary purpose of protecting the safety of participating patients and the integrity of the study.

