### **4.3.1. Discontinuation of Study Drug or Declining Procedural Assessments**

Reasons for discontinuation of study drug include any of the following:

- Significant violation of the protocol
- Adverse event
- Non-adherence to treatment regimen
- Pregnancy
- Lost to follow-up
- Other reason (non-adverse event), including confirmed positive test for ADA to cemdisiran
- Or, study is terminated by the Sponsor

Patients who are pregnant will be discontinued from study drug dosing immediately (see Section 6.7.5.2 for reporting and follow-up of pregnancy). A positive urine pregnancy test should be confirmed by a serum pregnancy test prior to discontinuing study drug.

Patients who discontinue study drug and/or decline procedural assessments should not be automatically removed from study. In general, patients who discontinue study drug dosing for any reason will be encouraged to remain on the study to complete the remaining assessments through the Week 36/EOS or Week 84/OLE EOS visit and safety follow-up so that their experience is captured in the final analyses.

If this occurs, the Investigator is to discuss with the patient the appropriate processes for discontinuation from study drug and must discuss with the patient the options for continuation of the Schedule of Assessments ([Table 2](#)), including different options for follow-up and collection of data (eg, in person, by phone, by mail, through family or friends, or from options not involving patient contact, such as communication with other treating physicians or from review of medical records), including endpoints and adverse events, and must document this decision in the patient's medical records.

If a patient discontinues dosing due to an AE, including SAEs, the event should be followed as described in Section [6.7.6](#). When a patient discontinues study drug dosing, the primary reason must be recorded in the eCRF. Patients who discontinue study drug and remain on study may receive treatment consistent with local standard practice for their disease per Investigator judgement, as applicable.

Patients who discontinue from study drug during the 36-week treatment period (defined as the time the first dose of study drug is administered on Study Day 1 through completion of the Week 36 assessments) will be encouraged to remain on the study and complete assessments through Week 36; they will also be asked to complete safety follow-up visits 13, 26, 39 and 52 weeks thereafter (see [Table 1](#)).

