#### **7.2.5.3. Exploratory Endpoints**

Change from baseline in exploratory efficacy variables will be summarized. Percent of patients in full clinical remission and incidence of ADA will be tabulated by treatments. Inferential

statistics for exploratory efficacy variables may be presented as needed. Details will be described in the SAP.

The slope of eGFR for the first 32 weeks will be estimated for each subject with the linear regression method using all assessment data during the period.

Descriptive statistics including the number of patients, mean, median, standard deviation (SD), interquartile range (Q1, Q3), minimum, and maximum values will be presented for continuous variables. Frequencies and percentages will be presented for categorical and ordinal variables.

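### The exploratory randomized-phase eGFR slope stops at Week 32 although a pre-dose, still-blinded Week 36 eGFR is scheduled; including it would give a modest gain in precision at no cost

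*Protocol*

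**What the plan says.** Section 2 lists as an exploratory endpoint "The slope of eGFR computed for the first 32 weeks using all assessments during the period". Section 6.4.3 repeats the window ("the slope of eGFR will be computed for the first 32 weeks and the entire study period"), and Section 7.2.5.3 adds the estimator: "The slope of eGFR for the first 32 weeks will be estimated for each subject with the linear regression method", with all assessments in that period used. The only other eGFR slope covers the whole study including the open-label extension (OLE), during which patients first assigned to placebo receive cemdisiran. The 32-week slope is therefore the only one that can compare the arms as randomized.

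The rest of the protocol places the end of the randomized period later:

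- Section 4.3.1 defines the 36-week treatment period as the time "the first dose of study drug is administered on Study Day 1 through completion of the Week 36 assessments".
- Section 3.6 keeps sites and patients blinded up to Week 36.
- Section 6.7.4 refers to a blinded dose at Week 32, and Section 3.1 states: "The first study drug administration of the OLE will be administered at Week 36". Patients who decline the OLE have their end-of-study visit at Week 36.
- Section 6.4.3 states: "Blood and urine samples for renal function assessments will be collected prior to administration of cemdisiran or placebo on dosing days".

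**The concern.** The Week 36 eGFR closes the last blinded 4-week dosing interval and is drawn before any open-label drug, so it belongs to the randomized comparison. A visit at the end of the window carries high leverage in a fitted slope. With about 18 and 9 evaluable patients and roughly eight months of follow-up, visit-to-visit eGFR noise is a large part of slope error, so omitting that visit gives up precision that the collected data would support.

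The document history suggests how the cut-off arose. In the first protocol version the treatment period, the blind and the start of the OLE all met at Week 32, so a 32-week window used every randomized visit. Amendment 1 moved those three to Week 36 and the slope window stayed where it was. That history explains the window; it is not itself an inconsistency in the current text. The protocol gives no reason for leaving Week 36 out of the slope.

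**Working it through.** **Availability of the Week 36 value.** The Amendment 2 schedule tables are not in the part of the protocol at hand, so the schedule is read from the Amendment 1 tables. The eGFR row of Table 1 has 18 marks, which fits screening (1), run-in (3), Day 1 to Week 32 (9), Week 36 (1) and safety follow-up (4). Table 2, for OLE entrants, starts eGFR at Week 36. For the current version, the Amendment 2 summary of changes confirms clinical laboratory tests from Week 36 in the OLE, and Table 5 lists eGFR under serum chemistry.

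**Patient numbers.** The protocol states no precision figure for the eGFR slope. Its only sample-size figure, in Section 7.1, is for log proteinuria: 27 patients at 2:1 (18 and 9) and log SD 0.597.

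- 90% CI width = 2 × 1.645 × 0.597 × √(1/18 + 1/9) = 0.802, against 0.80 stated.
- log(0.50/0.88) ± 0.401, back-transformed, gives reductions of 15.2% to 61.9%, against 15% and 62% stated.

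The figure reproduces, so 18 and 9 are used below.

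**Within-patient slope error.** Section 3.1 gives the spacing: "Patients will then return to the study center every 4 weeks after the start of study drug treatment period". For an ordinary least-squares slope with independent, equal-variance residuals, error variance is σ²/Sxx, where Sxx is the sum of squared deviations of the visit times from their mean.

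- Weeks 0 to 32 (9 visits): Sxx = 4² × 60 = 960 week².
- Weeks 0 to 36 (10 visits): Sxx = 4² × 82.5 = 1320 week².
- Ratio 960/1320 = 0.727, so error variance falls 27.3% and its square root falls 14.7%.

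This ratio needs no assumed SD. The reduction is 30.0% if Day 1 is excluded from both windows and 25.7% if the Week -2 value is added to both. With AR(1) residuals it is 26.2% at correlation 0.2, 24.5% at 0.4, 21.6% at 0.6 and 17.1% at 0.8.

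**Arm comparison.** True between-patient variation in slope is not reduced by a longer window. The SE of the arm difference is √(σ² × 52²/Sxx + τ²) × √(1/18 + 1/9), where σ is the visit SD, τ is the between-patient slope SD per year, and the last factor is 0.408. The protocol gives neither σ nor τ, so both are assumed.

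| σ (mL/min/1.73 m²) | τ (per year) | Slope variance, Week 32 | Slope variance, Week 36 | Fall in SE |
|---|---|---|---|---|
| 3 | 6 | 25.35 + 36 = 61.35 | 18.44 + 36 = 54.44 | 5.8% |
| 5 | 4 | 70.42 + 16 = 86.42 | 51.21 + 16 = 67.21 | 11.8% |
| 8 | 3 | 180.27 + 9 = 189.27 | 131.10 + 9 = 140.10 | 14.0% |

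In the limiting case σ = 5, τ = 0, the per-patient slope SE goes from 8.39 to 7.16 per year and the SE of the arm difference from 3.43 to 2.92. The 90% half-width (× 1.645) goes from about 5.6 to about 4.8 per year.

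**The case against.** The case for leaving the window alone has several parts.

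- **Week 32 does have meaning for eGFR.** Section 2 sets the change in eGFR and in creatinine clearance at Week 32, and Section 3.1 calls Week 32 the end of treatment. A slope over the same window is a coherent choice. This stands, and it is the reason to keep the 32-week slope as supportive. It is not a reason to omit a later randomized value from the only randomized slope.
- **The endpoint is exploratory.** Section 7.2.5.3 promises summaries of the exploratory variables and makes inferential statistics optional. This stands and limits the weight of the point. It does not make the window a matter for the statistical analysis plan, because the protocol fixes it in three sections.
- **Precision stays poor either way.** The half-widths above show that Week 36 does not make this comparison precise. This also stands.

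Some stronger readings are tempting but not supported:

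- A reader might take the 27% as the gain in the arm comparison. It is within-patient error variance under independent residuals, and the arm comparison gains less.
- A reader might infer that every Week 36 value is on randomized treatment. Section 4.3.1 encourages patients who stop study drug to stay through Week 36 and allows them local standard treatment. Their Week 36 value is off study drug, as are any earlier values after stopping, which the 32-week window already includes.
- A reader might conclude that the Week 36 value is thrown away. It still enters the whole-study slope and the eGFR change over time.
- A reader might see a contradiction or a bias. The window is stated consistently in all three sections, and shortening it does not of itself bias the comparison.

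**Conclusion.** The point holds as a minor, cost-free improvement. The extra precision depends on three things: the Week 36 eGFR being scheduled in the current tables as it was under Amendment 1, near-complete attendance at 4-weekly visits, and an approximately linear eGFR course over 36 weeks. Autocorrelation would reduce the gain: the 6% to 14% range for the arm-difference SE takes residuals as independent and rests on assumed SDs. The primary proteinuria analysis is untouched.

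**What to change.** In Sections 2, 6.4.3 and 7.2.5.3, and in the matching synopsis entry, define the randomized-phase slope as all eGFR values from Day 1 up to and including the pre-dose Week 36 sample. State that values after study drug discontinuation are treated at Week 36 in the same way as at earlier visits. Keep the 32-week slope as a supportive analysis aligned with the Week 32 eGFR change endpoint. The cost is wording only: no new visit, sample or patient.
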